8.7.1 Primary Objective

The primary objective of the study is to evaluate the feasibility to obtain a stable position of a ring of stimulation electrodes on the interatrial septum (stability performance).

Specifically, this primary objective of stable position of a ring of stimulation electrodes on the atrial septum also includes pacing threshold, pacing impedance, stability criterion and safety criterion variables. These data will be summarized in table format as count of data, count of missing data, mean, median, standard deviation, minimal and maximal values for continuous variables, and count of data and count of missing data, number and percentage per category, for categorical data.

∴

Description of stability performance assessed on *per patient basis* includes:

- Description of overall stability criterion (pacing threshold < 10 mA) (categorical variable)
- Description of the number of electrode pairs reaching the stability criterion;
- Description of safety criterion (no ventricular capture) (categorical variable)
- Description of the number of electrode pairs reaching the safety criterion

Description of stability performance assessed on *electrode pair basis*:

- Description of the pacing threshold (continuous variable)
- Description of the pacing impedance (continuous variable)
- Description of stability criterion (pacing threshold < 10 mA) (categorical variable)
- Description of safety criterion (ventricular capture) (categorical variable)

○

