5.2. Endpoints

5.2.1. Primary Endpoint

To assess Pacing Site Stability, the number of interatrial septal pacing electrodes which are successfully placed in a stable position, will be counted. A stable position in this study is defined as a location where the pacing threshold will be < 10 mA at a pacing pulse width of 1 msec. Stable pacing further requires that no ventricular capture will be induced during atrial stimulation at twice the atrial capture threshold.

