10.3. Assessment of Efficacy

During sinus rhythm, the number of cases in which the septal pacing electrodes are successfully placed in a stable position will be registered. A stable position is defined as a location where the atrial septal pacing threshold is lower than 10 mA at 1msec on all electrodes and where no ventricular capture at twice the atrial capture threshold is observed.

When the subject is in sinus rhythm after PV ablation, as a first step the atrial pacing threshold is determined, for each electrode, using a pulse width of 1 msec. Also, the impedance is determined for each electrode. During atrial stimulation at high threshold currents, ventricular capture may be possible and absence of ventricular capture at the atrial capture threshold measurement will be confirmed by stimulating from each electrode with twice the atrial capture threshold current (corresponding to specific electrode) from all electrodes at the same time using overdrive pacing at 20 bpm. If ventricular capture is observed during atrial stimulation at twice the atrial capture threshold, the position of the catheter on the septum will be changed and the tests for measuring thresholds, impedances and ventricular capture will be repeated until no ventricular capture occurs during atrial pacing at twice the atrial capture threshold. If it does not occur we will increase the current up to 20 mA and repeat sequence mentioned above. The maximum current will be that current, which does not induce ventricular capture when stimulating from all four electrodes at same time and is 20 mA or lower.

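### SAP 8.7.1 counts a threshold below 10 mA alone as stability and plans no joint summary with absence of ventricular capture, which protocol 10.3 makes part of a stable position

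*SAP*

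**What the plan says.** **Protocol 5.2.1 (primary endpoint).** Stable electrodes are to be counted. The section gives two statements in sequence: "A stable position in this study is defined as a location where the pacing threshold will be < 10 mA" (at a 1 msec pulse width), and then "Stable pacing further requires that no ventricular capture will be induced during atrial stimulation at twice the atrial capture threshold". Protocol 14.3 refers to section 5.2 for the primary endpoint and adds nothing.

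**Protocol 10.3 (assessment of efficacy).** Here the result is the number of cases with a stable position. The two conditions form one definition: the threshold must be "lower than 10 mA at 1msec on all electrodes and where no ventricular capture at twice the atrial capture threshold is observed".

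**SAP 8.7.1 (primary objective).** The objective "also includes pacing threshold, pacing impedance, stability criterion and safety criterion variables". Per patient, the SAP lists "Description of overall stability criterion (pacing threshold < 10 mA) (categorical variable" and, as a separate item, "Description of safety criterion (no ventricular capture) (categorical variable". Each has its own count of electrode pairs, and the same split is repeated per electrode pair. The safety item states no stimulation output.

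**SAP appendices.** Table 2 has separate rows for any capture, stability capture and ventricular capture. None is defined, and none is said to combine the two conditions. Table 3B lists the fields Pacingthreshold, StableAtrialCapture, Ventcapture, VentCaptureThreshold and StablePosition. StablePosition comes from the procedure form, and the SAP gives it neither a derivation nor a planned summary.

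**The concern.** The study's main result is how often a stable position is obtained. Under protocol 10.3 that needs both conditions at once. The SAP gives the name *stability* to one of them and never schedules the combination. A reader of the final report who takes the SAP's stability percentage as the stable-position result would be reading a figure that leaves out the ventricular-capture requirement.

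The study tests no hypothesis (protocol 14.1; SAP 7), so error rates and sample size are unaffected. What is at stake is what the primary descriptive figure means, and any difference can go only in the favourable direction.

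**Working it through.** The plan states no rate, power or target for this endpoint, so there is no figure to reproduce. The check compares definitions and bounds the difference.

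**1. Direction of the gap.** For one unit, one catheter position and one denominator n, let
- A = threshold below 10 mA at 1 msec on all tested electrodes (the SAP stability criterion, reading its per-patient *overall* item as all electrodes);
- B = no ventricular capture at twice the atrial threshold.

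The protocol 10.3 result is the count of A and B together. Since that set lies inside A, count(A and B) ≤ count(A). The difference is d = the number meeting A but not B, and the gap is d/n.

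**2. Size.** Take n = 15, the number of complete datasets that protocol 8.1 seeks for the stability analysis (assumed here to be the per-protocol set).

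| Discordant patients d | Gap d/15 |
|---|---|
| 0 | 0 points |
| 1 | 1/15 = 6.7 points |
| 2 | 2/15 = 13.3 points |

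The documents give no basis for choosing d.

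**3. When d = 0.** Under protocol 10.3, if ventricular capture is seen at twice the threshold, the catheter is moved and "the tests for measuring thresholds, impedances and ventricular capture will be repeated until no ventricular capture occurs". If this always succeeds and the final position is analysed, B holds for every patient and the gap vanishes. The SAP does not say which position is analysed.

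**4. Do the two separate lines give the joint result?** Two counts a and b out of n bound the joint count between max(0, a + b − n) and min(a, b). With assumed counts of 12 and 12 out of 15, the lower bound is 12 + 12 − 15 = 9 (60%) and the upper is 12 (80%). If either count is 15, the joint count is fixed exactly. The 12-and-12 case only shows that separate totals are not enough in general. It is not a forecast, because it ignores the repositioning rule in step 3.

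**5. The unstated output.** After the test at twice the threshold, protocol 10.3 continues: "If it does not occur we will increase the current up to 20 mA and repeat sequence mentioned above". On the natural reading, this step-up follows when no ventricular capture has been seen. If the threshold T is below 10 mA, then 2T is below 20 mA, so the step-up goes beyond the level in the definition. With T = 4 mA (assumption), the defining test is at 8 mA and the step-up covers 8 to 20 mA. Ventricular capture seen only in that range could be recorded as a failure of the SAP safety criterion although condition B is met.

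**6. Can the data supply the joint result?** Yes, where units agree. Condition B fails if Ventcapture is yes and VentCaptureThreshold is at or below twice Pacingthreshold; it holds if capture is absent or appears only above that value. Both fields allow mA or V, so the comparison needs the same unit.

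**The case against.** The best defence is that protocol 14.3 points to section 5.2, not to 10.3. Section 5.2.1 defines a stable position by threshold and then adds ventricular capture as a further requirement for stable pacing. The SAP mirrors that two-part structure and keeps both parts under *stability performance*, per patient and per electrode pair. SAP 8.2 also promises subject data listings, so with about 15 subjects a reader could pick out any discordant patient. No success threshold or decision depends on the figure.

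Most of this stands, and it limits the point. A reader might infer any of three stronger things, and the documents support none of them:

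- *The SAP drops ventricular capture from the primary objective.* It does not; it reports it separately under that objective.
- *The primary figure will be inflated.* This cannot be said. The repositioning rule aims at d = 0, and protocol section 10 expects most subjects to be in sinus rhythm, where that rule applies directly.
- *The protocol result could not be recovered from the data.* Step 6 shows that the listed fields allow it where units match.

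Nor can it be said that StablePosition is undefined everywhere: the procedure form is not among the documents and may define it.

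What the defence does not remove is that section 5.2.1 itself attaches the second condition at a stated output, that 10.3 joins the two outright, and that a listing is not a planned summary. The difference in wording between 5.2.1 and 10.3 is a reason to report the joint result alongside its parts, since that serves either reading.

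**Conclusion.** The point holds as a gap in the planned primary summary. The SAP's stability figure is not the stable-position result of protocol 10.3. It can equal or exceed that result and cannot be lower, by 6.7 points for each discordant patient out of 15 and by zero if there are none. This rests on comparing the same unit, catheter position and denominator. It also assumes a per-protocol set of 15 and that the per-patient SAP item means all tested electrodes, which the SAP does not spell out. Part of the cause is the protocol's own difference in wording between 5.2.1 and 10.3.

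One limit applies to subjects still in AF after isolation. Protocol 10.3 runs their ventricular-capture test before thresholds are measured in sinus rhythm, and the documents do not describe how the two are paired. It is worth correcting before analysis, but it affects interpretation only.

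**What to change.** Add one new derived variable to SAP 8.7.1 and Table 2, leaving the form-sourced StablePosition field unaltered so that nothing recorded at the sites is overwritten:

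- **Per patient:** the proportion of patients who, at the final catheter position, have a threshold below 10 mA at 1 msec on all tested electrodes and no ventricular capture at twice the atrial threshold.
- **Electrode count (protocol 5.2.1):** protocol 10.3 tests ventricular capture with all electrodes stimulated together, so treat that result as a condition on the patient and position. The count is then the number of electrodes below 10 mA at a position without such capture.

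Keep the separate threshold and ventricular-capture lines as supportive, and state that the ventricular-capture line refers to twice the threshold. Say in one sentence how the two measurements are paired for subjects tested in AF. Reconcile the wording of protocol 5.2.1 and 10.3.

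The cost is one derived variable, one or two table rows and a possibly slightly lower primary figure. No new measurement is needed. Table 3B has no field for the positioning attempt, so if several positions are recorded for a patient, the final one must be identifiable.

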8.7.2 Secondary Objectives

The secondary objectives of this study are:

Localized Atrial Capture: evaluate if during the rapid pacing phase at a given coupling from multiple electrodes on the interatrial septum, local atrial capture can be observed during AF. Atrial capture is obtained from the electrocardiogram recordings from the interatrial septal catheter, the coronary sinus catheter and the right atrial catheter. Capture is defined as a consistent temporal association of an electrocardiogram signal and the pacing stimulus.

Initially interatrial septal pacing electrodes will be identified by its electrode number. The electrode number will be translated by the project scientist with support of a clinician trained and experienced in the AF Ablation procedure into an anatomic location. This translation process will be done by the scientist and the clinician based on fluoroscopy recordings collected during the procedure. The data will be entered into the analysis database. The position will be consistently assigned into a clockwise scheme starting e.g. from cranial/superior at 12:00.

Atrial capture analysis will be based on the electrocardiograms recorded from the interatrial septal electrodes, the coronary sinus electrodes and the right atrial electrodes. The analysis will be performed automatically using Matlab and the results will be entered into the analysis database by the project scientist.

Capture will be classified as:

- 1) any atrial capture on a specific electrode during the atrial septal pacing period
- 2) % temporal atrial capture as an estimate of how many of the delivered interatrial pulses lead to an atrial capture on any sensing electrode
- 3) % spatial atrial capture as an estimate of on how many of the monitoring electrodes will be able to detect atrial capture

The anatomical distance will between any CS and RA electrode and the interatrial septum will be estimated by a clinician trained and experienced in the AF ablation procedure. The distance estimate will be obtained based on the fluoroscopic recordings. The inter-electrode distance of the diagnostic catheters will be used to help quantifying the distance in cm.

AF Termination Scheme: evaluate if AF termination was observed during the experimental atrial septal pacing scheme from multiple electrodes on the interatrial septum. Acute procedural AF termination was defined as termination of AF to SR or a regular atrial tachycardia/flutter during the experimental pacing procedure without re-initiation of atrial fibrillation during the experimental pacing scheme.

AF termination will be described as the count and frequency of any AF termination
Subgroup descriptions and summary of atrial capture and AF termination will be done for:

- Atrial fibrillation group (SR vs AF group)
- Catheter type (Achieve vs. Lasso or other)
- Anatomical electrode position
- Atrial Cycle Length

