Next, atrial fibrillation will be induced by rapid atrial pacing, gradually elevating the atrial pacing rate until 1:1 atrial capture is lost. AF cycle length will be determined by recording the atrial electrogram on the septum. Stimulation on the septum from all electrodes starts at the current defined above, using various pacing cycle length (PCL), being percentages of AFCL and will last for 10 to 30 seconds, depending on when capture occurs, followed, if feasible, by slow pacing using an interval of 130% of AF for one cycle followed by 1.5 second of 180% of AF Cycle length at maximum output which did not induce ventricular capture (20 mA or lower). Multiple PCLs will be used to start the pacing sequence. During each stimulation sequence, corresponding to each PCL, atrial capture at each recording electrode will be assessed. The optimal parameters for stimulation will be used to determine local capture for all electrodes.

When the subject will still be in AF after successful pulmonary vein isolation the ventricular capture tests will be performed first during atrial fibrillation (as described above for subject in sinus rhythm). Then, AF cycle length will be determined and

the two-stage atrial pacing scheme as described above will be performed. If delivery of the two-stage atrial pacing scheme either will not be feasible or not stop the AF, the subject will be externally cardioverted under deep sedation as would have been done as common practice at the end of the ablation procedure. Next, during sinus rhythm pacing thresholds and impedances on all septal catheter electrodes will be determined.

To assess if the two-stage pacing scheme can terminate AF, the surface ECG will be analyzed and PCL and stimulation current will be noted.

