5.2 Secondary Objectives

The secondary objectives of this study are:

- Localized Atrial Capture: evaluate if during the rapid pacing phase of the two-stage septal pacing scheme (rapid pacing followed by a step-wise transition to slow-pacing) from multiple electrodes on the interatrial septum, local atrial capture can be observed during atrial fibrillation.
- AF Termination Scheme: evaluate if AF termination can be obtained using a dual-stage septal pacing scheme (rapid pacing followed by a step-wise transition to slow-pacing) from multiple electrodes on the interatrial septum.

6. Investigation Plan

The AF Septal Pacing study is a non-randomized, non-controlled, acute, single-arm research study that will be conducted in up to three European centers.

Approximately 15 subjects with AF indicated for ablation of the pulmonary vein will be enrolled in the study. Participants will attend the Baseline visit and the Procedure visit that can occur on the same day. Since it is an acute study, no follow-up visit will occur. The research procedure will be performed during an already scheduled ablation procedure.

The point of enrollment is the time when subject signs and dates the Informed Consent Form (ICF). At that point, the subject is considered included in the study.

Selection of subjects, treatment of subjects, and evaluation of study data are potential sources of bias. Methods incorporated in the study design to minimize potential bias include (but are not limited to):

- Patients will be screened to confirm eligibility for enrollment in accordance to the inclusion/exclusion criteria.
- Subject demographics will be collected at baseline on possible differences that may affect the primary objective.
- All study clinicians, participating site personnel, and Medtronic personnel will be trained on their respective pertinent role of the study using standardized training materials.

No control group, no randomization and no blinding will be used in this Study.

Clinical Study Flowchart is summarized in Figure 2:

[figure not shown]

Figure2: Standard ablation procedure (left side) and experimental procedure (right side, yellow boxes) performed during standard procedures.

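### The capture scores in SAP 8.7.2 omit the rapid-phase and during-AF limits of their own objective, so slow-stage or post-AF stimuli can count as capture of AF

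*SAP*

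**What the plan says.** SAP 5.2 ties the first secondary objective to the rapid pacing phase and asks whether, "from multiple electrodes on the interatrial septum, local atrial capture can be observed during atrial fibrillation". SAP 8.7.2 opens in the same way, asking whether "local atrial capture can be observed during AF" in the rapid phase.

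The operational rules in SAP 8.7.2 read differently:

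- Definition: "Capture is defined as a consistent temporal association of an electrocardiogram signal and the pacing stimulus". The rhythm at the time of the stimulus is not a condition.
- Score 1: "any atrial capture on a specific electrode during the atrial septal pacing period".
- Score 2, a percentage over time: "how many of the delivered interatrial pulses lead to an atrial capture on any sensing electrode".
- Score 3, a percentage over space: "spatial atrial capture as an estimate of on how many of the monitoring electrodes will be able to detect atrial capture".

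Protocol 10.3 describes a stimulation sequence of 10 to 30 s of rapid pacing, "followed, if feasible, by slow pacing using an interval of 130% of AF for one cycle followed by 1.5 second of 180" percent of the AF cycle length (AFCL). SAP 8.7.2 defines termination as "termination of AF to SR or a regular atrial tachycardia/flutter during the experimental pacing procedure", provided AF does not restart during the scheme.

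SAP Table 6 holds one capture flag and one capture percentage per sensing electrode and run. Although Tables 5 and 6 both have AF termination in their titles, neither lists a termination flag, a termination time or a pacing phase.

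**The concern.** The target is whether septal pacing can take hold of fibrillating tissue. Once AF has stopped, a stimulus that paces the atrium in sinus rhythm or a regular tachycardia answers a different question, yet it meets the SAP's definition of capture. Slow-stage stimuli also fall outside the stated target, whatever the rhythm.

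If such stimuli are scored, reported capture is too high, and selectively so in the runs in which AF stopped. Anyone reading the capture and termination summaries side by side could then see a link between the two that comes partly from the scoring. The scoring is automated in Matlab, so the code needs an explicit window, and the output tables as listed would not show which window had been used.

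**Working it through.** The plan gives no capture figure and no sample-size calculation, so there is nothing to reproduce. The check compares the texts and then counts pulses.

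**1. Which window do the texts imply?** The pacing period in score 1 is not defined. Three places favour a wide window. Protocol 10.3 assesses capture over each stimulation sequence, having just described a sequence that includes the slow stage. The second capture endpoint in Protocol 5.2.2 describes the scheme with its slow stage. The SAP's termination definition, by excluding re-initiation, allows for scheme time after AF has stopped. No text ends either the rapid phase or the capture window at AF termination.

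**2. Inputs.**

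- Rapid phase T = 10 to 30 s (Protocol 5.2.2 and 10.3).
- Pacing interval f = 62 to 70% of AFCL (computer-model scheme, SAP 4; the human study uses various intervals).
- Slow stage: one stimulus at 130% AFCL, then 1.5 s at 180%.
- AFCL = 100 to 400 ms (field range in Tables 5 and 6).
- Assumed, not in the documents: capture rate c during AF (0, 30%, 50%) and capture rate q after AF stops (100% or 50%).

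**3. Score 2 if AF ends at the slow stage.** Rapid pulses R = floor(T/(f × AFCL)). Slow pulses S = 1 + floor(1.5 s/(1.8 × AFCL)). If every slow pulse captures, score 2 = (cR + S)/(R + S).

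- AFCL 200 ms, 64%, 30 s: R = floor(30000/128) = 234 and S = 1 + floor(1500/360) = 5, a slow share of 5/239 = 2.1%. Score 2 moves from 0 to 2.1%, from 30 to 31.5%, or from 50 to 51.0%.
- Smallest share (100 ms, 62%, 30 s): 9/(483 + 9) = 1.8%.
- Largest share (400 ms, 70%, 10 s): 3/(35 + 3) = 7.9%. Here c = 30% becomes (10.5 + 3)/38 = 35.5%.

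The rise is therefore about 2 to 8 points when c = 0, and smaller for larger c.

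**4. Score 2 if AF stops inside the rapid phase.** If AF stops after a fraction t of the pulses and pacing continues (slow stage ignored), score 2 = ct + q(1 − t). With c = 30%:

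| t | q = 100% | q = 50% |
|---|---|---|
| 5% | 96.5% | 49.0% |
| 10% | 93.0% | 48.0% |
| 25% | 82.5% | 45.0% |
| 50% | 65.0% | 40.0% |
| 90% | 37.0% | 32.0% |

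With q = 100%, a score of at least 95% needs t ≤ 0.05/(1 − c), which is 5%, 7.1% or 10% of the pulses for c = 0, 30% or 50%. With q = 50%, score 2 never exceeds 50% in these scenarios.

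**5. Scores 1 and 3.** If one captured pulse is enough for score 1 and pulses are independent, k pulses after AF give a positive electrode with probability 1 − (1 − q)^k. For k = 5 and q = 50% this is 1 − 0.5^5 = 96.9%. Score 3 can reach 100% if every monitored electrode follows a paced beat.

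**6. Score 2 if AF does not stop.** Only the slow-stage pulses are out of place. Their share is 1.8 to 7.9%, so score 2 cannot move by more than that, and it can move either way.

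**The case against.** The best defence is that SAP 8.7.2 states both limits before it lists the scores, so the scores may inherit them. The undefined pacing period could mean the rapid phase alone: the SAP speaks of a pacing scheme when it discusses termination, and Table 6 has a single paced-interval field per run, which suits a rapid-only run. This stands as a reason to call the fault an objective not carried into its scoring rules. It does not close the gap, because even a rapid-only window would include rapid pulses given after AF has stopped.

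A reader might infer that any run that terminates AF scores full capture almost automatically. The documents do not support that:

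- Score 2 gets there only if AF stops within roughly the first 5 to 10% of pulses and nearly every later pulse captures.
- Capture at rapid intervals outside AF is not assured. Protocol 10.3 induces AF by pacing faster until 1:1 capture is lost.
- The mapping experiments cited in Protocol 4.1 and SAP 4 saw no termination by rapid pacing.
- The definition asks for a consistent association. Whether about five slow pulses satisfy that is open, and this also limits the 96.9% figure.
- The scheme figure shows rapid pacing continuing until local capture is achieved, so runs that reach the slow stage will often be positive already. Electrodes that missed capture in the rapid phase, such as those in the right atrium or coronary sinus, could still change.

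A reader might also infer that the plan would present false evidence that capture leads to termination. No analysis of capture by termination is planned and no hypothesis is tested. The risk lies in informal reading of the two summaries together.

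**Conclusion.** The concern holds as a gap between objective and scoring. As written, scores 1 to 3 can count slow-stage and post-AF stimuli as capture of AF, and the listed tables could not reveal it. The bias is upward and arises mainly in runs in which AF stops. Score 1 is the most exposed and score 3 possibly so. Score 2 rises by at most about 2 to 8 points if AF ends at the slow stage. It rises by more only with early termination in the rapid phase and good capture afterwards.

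These sizes rest on the assumed c and q and on the computer-model pacing intervals. The number of affected runs is unknown: the only termination figure in the documents is a computer-model maximum of 29% at the optimal interval (Protocol 4.1), which is not a human rate. If no run terminates, the effect is small. The study is descriptive, so no error rate is affected, only the reported capture summaries. This is a cheap improvement, best made before the final analysis.

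**What to change.** In SAP 8.7.2, state that scores 1 to 3 use only rapid-phase stimuli delivered while AF is present: from the first rapid stimulus to the earlier of the end of the rapid phase and AF termination, as read from the surface ECG and the right atrial and coronary sinus electrograms. Report capture in the slow stage and after termination in separate rows. Add pacing phase and time of AF termination to Table 6. Give the number of stimuli behind each percentage, since a run in which AF stops early will contribute few.

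The cost is the SAP wording, two data fields and a cut-off in the Matlab script. Protocol 7.1 has the signals recorded throughout the procedure, so no new data are needed and pacing does not change. The downside is slightly fewer pulses per run and a possibly lower capture figure.
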